8.3. Primary End Point Variables

Numbers of men approached for CHRONOS-A and CHRONOS-B per month per centre

- Numbers of men recruited to CHRONOS-A and CHRONOS-B per month per centre
- Numbers of men randomised to CHRONOS-A and CHRONOS-B per month per centre
- Total number of men completing each stage for each treatment arm of CHRONOS-A and CHRONOS-B
- Number of days between consent and randomisation in days:
 - o Date of consent
 - o Date of randomisation
- Number of days between randomisation and start of treatment (CHRONOS-A and CHRONOS-B):
 - Date of randomisation
 - o Date of focal therapy (CHRONOS-A (Focal arm) and CHRONOS-B)
 - Date of treatment visit (CHRONOS-A (Radical arm))
- Treatment form information and date of visit (collected at Visit 2) (CHRONOS-A and CHRONOS-B)
- Focal therapy information (collected at Visit 2) (Focal arm of CHRONOS-A and CHRONOS-B):
 - Date of Focal Therapy
 - o Form of Focal therapy performed
 - o Focal therapy ablation schema
 - Seminal vesicle treatment
- Radiotherapy/Prostatectomy information (collected at Visit 2) (Radical therapy arm of CHRONOS-A):
 - Radiotherapy/Brachytherapy Log (CHRONOS-A (Radical therapy)):
 - Form of radiation treatment undergone
 - Radiotherapy treatment details (which radiotherapy regime was performed, whether the patient had lymph node radiotherapy, whether patient completed their radiotherapy course)
 - Brachytherapy treatment details (whether the patient underwent treatment as planned, whether the patient underwent radiotherapy boost alongside brachytherapy, confirmed on post-procedure dosimetry).
 - Prostatectomy Log (CHRONOS-A (Radical therapy)):
 - Whether the patient underwent radical prostatectomy or not.
- Neoadjuvant drug information (collected at Visit 2) (CHRONOS-B):
 - Date neoadjuvant treatment was commenced
 - o Whether empty blister pack has been returned
 - Date empty blister pack was returned
 - Registered protocol deviations for drug compliance
 - Registered protocol deviations which state that the drug was taken for less than 8 weeks
- Number of days between consecutive visits:
 - Date of visit
- Number of days between randomisation and start of neoadjuvant drug treatment (CHRONOS-B):
 - Date of randomisation
 - Date neoadjuvant drug treatment commenced (CHRONOS-B)
- Number of days between start of neoadjuvant drug treatment and start of focal therapy (CHRONOS-B)
- Occurrence of adverse events not listed in Appendix 1 (see Section).

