6.2. Treatment Groups

6.2.1. CHRONOS-A

- Arm 1 (Control arm): Radical therapy (prostatectomy or radiotherapy [external beam or brachytherapy]). The type of radical therapy will be determined by physician or patient preference.
 - o In radiotherapy patients, neoadjuvant ADT permitted and if given, minimum 3 months and maximum 6 months duration.
 - We anticipate lymph node treatment in this group is not required but for cause lymph node treatment will be permissible if strong clinical preference is demonstrated.
 - If an extended lymph node dissection is anticipated this will need to be discussed in a central review by the surgery subgroup.
 - As per Radiotherapy Trials Quality Assurance (RTTQA) centres and physicians delivering radiotherapy will need to be approved.
 - o Radiotherapy detailed protocols will be set out in a separate SOP.
 - Surgeons and surgical centres currently are approved as a national commissioning programme so any centre or surgeon permitted to carry out radical prostatectomy in standard NHS practice will be permitted to deliver prostatectomy within this trial.
 - Prostatectomy details will be set out in a separate SOP.
- Arm 2 (Intervention arm): Focal therapy alone (high intensity focused ultrasound [HIFU] or cryotherapy or other validated energy modality as per physician/patient decision/choice. Other energy modality will only be added after TSC and TMG approval and a substantial amendment approved by all required bodies.

- A second treatment either in-field or out-of-field will be permitted either after the MRI and control biopsy showing clinically significant cancer at 12-months or due to suspicion of residual or new contralateral disease at a future date with a positive biopsy for clinically significant cancer.
- Cryotherapy can be used after HIFU and HIFU can be used after cryotherapy. This second focal therapy session will be part of the focal therapy intervention
- o Focal therapy details will be set out in a separate SOP.

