6.7.2. Visit Schedule

The design and number of visits mirror the standard of care pathway for patients undergoing either focal therapy or radical therapy, so that additional patient burden is minimal. Prior to enrolment, all patients will have undergone a Prostate Specific Antigen (PSA) blood test, a diagnostic prostate MRI and prostate biopsies. A standard of care (SOC) multi-disciplinary team case review will precede any discussion with the patient on all suitable treatment options and trial suitability. After an MDT discussion confirming suitability for FT and/or radical therapy has taken place, a patient information sheet (PIS) explaining the study will be provided, after which patients will be given a minimum of 24 hours to consider taking part. We aim for consent to be taken during a SOC appointment, or an additional consultation via phone, or in person. Randomisation will take place during the visit in which consent is taken along with any required neoadjuvant therapy, as allocated via randomisation, to be prescribed and within 24 hours of receiving the prescription. Time from randomisation will be used to define progression free survival and failure free survival. The end of treatment is defined as the final part of any intervention. For radiotherapy, this is the final radiation fraction completed and for prostatectomy and focal therapy the point at which the catheter is removed. Therefore, the follow-up visits noted below will start from these time-points, which will define the date of first follow-up visit (visit 2).

	Screening & Consent	Visit						
Visit	1	2	3	4	5	6	7	6 monthly visits until last visit 60 months after visit 2
Months				se below spec ach arm	ify the	e mon	ths af	ter the completion of each treatment
		0	3	12	18	24	30	31-60. Visits 4 onwards can be telephone consultations in order to note clinical outcomes although MRI scans and biopsies where done will require physical visits to the hospital
Informed Consent and enrolment into either CHRONOS A or CHRONOS B	Х							
Inclusion & exclusion criteria checked, including concomitant medication review	х							
Randomisation	x							
Prescription of neo- adjuvant therapy	X (if randomised to such arm)							Within 24hrs of randomisation
PSA blood test			Х	Х	Х	Х	Х	X (6 monthly)
Prostate Contrast MRI	X (if randomised to focal therapy and no contrast given during diagnostic scan – to have prior to visit 2)							
Prostate mpMRI				X (focal therapy arms)				

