9.3. Primary End Point Analysis

The proportions of patients who opted for CHRONOS-A and CHRONOS-B will be reported.

The primary analysis of the internal pilot will calculate the mean number of patients recruited and randomised per month, per centre (including only the months in which the centre is open and recruiting). Overall recruitment and randomisation rates will also be calculated, along with their corresponding 95% confidence intervals. Recruitment rate is calculated as the number of participants recruited out of the total number approached. Randomisation rate is calculated as the number of participants randomised out of the total number recruited. Graphs displaying the recruitment and randomisation rates over time will be presented. A graph displaying the actual vs target recruitment rates will also be presented. These analyses will be conducted for CHRONOS-A and CHRONOS-B.

Compliance will be summarised using the CONSORT diagram for the internal pilot (see Section 1.1.1) which includes, the number of men who have withdrawn or been lost to follow-up (with reasons), and the number who completed each stage within each treatment arm. There will be a separate CONSORT for CHRONOS-A and CHRONOS-B.

Summary statistics for time between consent and randomisation, and randomisation and treatment will be presented by treatment arm. Summary statistics will also be presented for time between consecutive visits, by treatment arm.

For CHRONOS-B only, summary statistics will also be presented for time between randomisation and start of neoadjuvant treatment, and time between start of neoadjuvant treatment and start of focal therapy.

Treatment, for CHRONOS-A and CHRONOS-B, is recorded at Visit 2 (Treatment Visit). For focal therapy arms (CHRONOS-A (Focal arm) and CHRONOS-B) treatment is recorded by date of treatment and completed treatment details at Visit 2. For the radical arm of CHRONOS-A, treatment is recorded by date of visit 2 and completed treatment details on Radiotherapy/Brachytherapy Log and Prostatectomy Log at Visit 2. The proportions of patients in each treatment arm who underwent treatment will be presented, along with their corresponding 95% confidence intervals.

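### In CHRONOS-A the SAP times start of treatment to the focal procedure in one arm but to Visit 2, dated from the end of treatment, in the radical arm

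*SAP*

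**What the plan says.** SAP 8.3 lists the variable as "Number of days between randomisation and start of treatment (CHRONOS-A and CHRONOS-B" and then names its component dates. The end date for the focal arm is "Date of focal therapy (CHRONOS-A (Focal arm) and CHRONOS-B". For the radical arm it is "Date of treatment visit (CHRONOS-A (Radical arm".

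SAP 9.3 says that treatment "is recorded at Visit 2 (Treatment Visit", and adds: "For the radical arm of CHRONOS-A, treatment is recorded by date of visit 2".

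SAP 6.7.2, in wording shared with Protocol 5.7, defines the end of treatment: "For radiotherapy, this is the final radiation fraction completed and for prostatectomy and focal therapy the point at which the catheter is removed". It says that follow-up runs from these time-points, "which will define the date of first follow-up visit (visit 2". The visit table places Visit 2 at month 0 after completion of treatment, with a window of plus or minus 4 weeks.

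SAP 9.2 and 9.3 place the interval in the primary end-point analysis, by arm. Table 2.4 shows it for Focal, Radical and Total. SAP 10.1 splits men at 05/03/2020 by their radical or focal treatment start date. That split feeds Tables 6.11 and 6.12 (the interval) and Tables 6.25 and 6.26 (treatment compliance).

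**The concern.** One label covers two different clinical moments. The focal arm is timed to the delivery of treatment and the radical arm, on the written definitions, to its completion. SAP 6.7.2 applies an end-of-treatment rule to focal therapy as well, but 8.3 uses a separate focal therapy date in place of the visit date. It lists no counterpart for the radical arm: the items from the Radiotherapy/Brachytherapy and Prostatectomy Logs include no first-fraction, implant or operation date. The asymmetry is therefore in the variable list itself.

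At stake is a planning figure. Time to treatment by arm is something a pilot should hand to the main stage. If the radical figure contains treatment duration, part of it could be read as slow access to radical treatment, and the true wait in that arm would not be reported.

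**Working it through.** **Step 1: follow the dates.**

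| | Focal arm | Radical arm |
|---|---|---|
| Label (SAP 8.3) | start of treatment | start of treatment |
| Date used (SAP 8.3) | focal therapy | treatment visit |
| Which visit (SAP 9.3) | not needed | Visit 2 |
| How Visit 2 is dated (SAP 6.7.2) | not used here | last fraction, or catheter removal |

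**Step 2: the bias in symbols.** Let W be the wait from randomisation to the true start of treatment, and D the time from that start to Visit 2. The focal figure is W(focal). The radical figure is W(radical) + D. The reported difference is therefore [W(radical) − W(focal)] + D. As treatment cannot end before it starts, D is not negative, and the bias is the mean of D.

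**Step 3: size.** The documents give no figure to reproduce. For a mix of external beam radiotherapy and surgery,

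mean D = p × L + (1 − p) × C,

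where p is the radiotherapy share, L the days from first to last fraction and C the catheter days after prostatectomy. All three are assumptions: L = 7, 28 or 56; C = 7 or 14; p = 0.25, 0.50 or 0.75.

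| L | C | p = 0.25 | p = 0.50 | p = 0.75 |
|---|---|---|---|---|
| 7 | 7 | 7.00 | 7.00 | 7.00 |
| 7 | 14 | 12.25 | 10.50 | 8.75 |
| 28 | 7 | 12.25 | 17.50 | 22.75 |
| 28 | 14 | 17.50 | 21.00 | 24.50 |
| 56 | 7 | 19.25 | 31.50 | 43.75 |
| 56 | 14 | 24.50 | 35.00 | 45.50 |

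For example, 0.50 × 28 + 0.50 × 14 = 21 days. The range is 7 to 45.5 days, roughly 1 to 6 weeks. Brachytherapy is not modelled. If D is taken as close to zero after an implant, a brachytherapy share b multiplies these figures by (1 − b).

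**Step 4: the Total column.** With the planned 30 men per arm, the pooled mean is raised by half the radical bias: 0.5 × 21 = 10.5 days in the middle case, and 3.5 to 22.75 days over the range.

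**Step 5: would it be visible?** The SAP plans no test, so this is only a gauge of signal against noise. Suppose true waits are equal, n = 30 per arm and the artefact is 21 days. The chance of a two-sided 5% difference is Φ(21 / (SD × √(2/30)) − 1.96). With an assumed SD of 20, 30 or 45 days this is 0.98, 0.77 or 0.44.

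**Step 6: after the correction.** With a start date in both arms, D drops out and the spurious difference is 0 days when true waits are equal.

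**Step 7: the Covid split.** SAP 10.1 needs a radical treatment start date, which 8.3 does not list. If Visit 2 is substituted, a man who started radical treatment before 05/03/2020 and finished on or after that date falls in the later period. How many men this affects cannot be worked out from the documents.

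**The case against.** The strongest reply is that Visit 2 is not only an end-of-treatment date in these documents. SAP 9.3 calls it the treatment visit, the schedule puts the treatment row in its column with a note that length varies, SAP 5.1 refers to Visit 2/3, and Table 2.9 cites Visit 3. If sites enter the start of treatment as Visit 2, the bias disappears. This stands as a limit on certainty. It does not rescue the definition, because the only text that dates Visit 2 ties it to the end of treatment, and the figure would otherwise depend on each site's reading.

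Table 2.6 already compares Visit 1 to Visit 2 by arm on one anchor. That is a partial safeguard, but it does not isolate the wait. Because randomisation is planned for the consent visit, the radical column of Table 2.4 would largely repeat it.

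A reader might also infer more than the documents support:

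- **That the radical arm is bound to look slower.** The bias is upward, but the observed order also depends on the true waits.
- **That neoadjuvant ADT adds to the error.** SAP 6.2.1 says "neoadjuvant ADT permitted and if given, minimum 3 months and maximum 6 months duration", about 91 to 183 days at 30.4375 days per month. Those days precede the first fraction, so they would stay in the interval after the correction too. CHRONOS-B likewise counts its neoadjuvant drug period before focal therapy, though it also reports the components separately. What is missing is a statement of whether ADT counts as the start.
- **That the pilot's decision is affected.** Progression rests on the recruitment rate (SAP 11) and on treatment and drug compliance (SAP 9.3). This interval has no threshold.
- **That PFS is distorted.** PFS runs from randomisation, and this feasibility SAP contains no PFS analysis.
- **That SAP 10 certainly carries the same error.** SAP 10.1 asks for a start date and leaves it undefined for the radical arm. Using Visit 2 there is a risk, although SAP 10.4 repeats that radical treatment is recorded by the Visit 2 date.

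**Conclusion.** The point holds as a fault in a written definition. Read as it stands, the SAP gives a radical-arm interval that includes treatment duration, is not comparable with the focal arm, and makes the Total in Table 2.4 a mixture. The overstatement of the radical mean is about 7 to 46 days, resting wholly on assumed course lengths, catheter times and modality shares. It is largest for fractionated external beam radiotherapy and smaller for surgery or brachytherapy. The direction follows from the definitions; the size, and whether it occurs in practice, depend on how sites date Visit 2. The 4-week visit window adds further slack.

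The consequence is a misleading descriptive summary within the primary end-point analysis, and possible misplacement of some men in the Covid split. CHRONOS-B is not affected, since all its arms use the focal therapy date. The definition should be corrected before the pilot tables are produced.

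**What to change.** In SAP 8.3, 9.3 and 10.1, and in Tables 2.4, 6.11 and 6.12:

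- define start of radical treatment as the date of the first radiotherapy fraction, the brachytherapy implant or the operation;
- state whether permitted neoadjuvant ADT counts as the start of treatment;
- use Visit 2 only as the end-of-treatment anchor for follow-up, and make its label consistent across the SAP.

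No clinical procedure changes. The cost is SAP wording plus a few dates. SAP 8.3 lists none of them in the radical logs, so they must be added to the eCRF or retrieved from hospital records, where they should be routine entries. The effort is modest with 30 radical-arm men planned in the pilot.

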7.3 Serious Adverse Events (SAE)

i. Definition of SAE

An SAE is defined as any event that:

- Results in death;
- Is life-threatening*;
- Requires hospitalisation or prolongation of existing inpatient hospitalisation**;
- Results in persistent or significant disability or incapacity;
- Is a congenital abnormality or birth defect;

^{* &}quot;Life-threatening" in the definition of "serious" refers to an event in which the subject was at risk of death at the time of the event; it does not refer to an event which hypothetically might have caused death if it were more severe.

Short Title: IP4 - CHRONOS	Protocol No: 19CX5006	Sponsor: Imperial College London	Version: 5.0 Date: 13 th July 2022
			10 daily 2022

** "Hospitalisation" means any unexpected admission to a hospital department. It does not usually apply to scheduled admissions that were planned before study inclusion or visits to casualty (without admission).

Medical judgement should be exercised in deciding whether an adverse event/reaction is serious in other situations. Important adverse events/reactions that are not immediately life-threatening, or do not result in death or hospitalisation but may jeopardise a subject, or may require intervention to prevent one of the other outcomes listed in the definition above should also be considered serious.

List of expected adverse events that may require hospitalisation and serious adverse events that will not require reporting as SAEs but will be collected:

- Urinary retention and any admission required for this
- Urinary tract infection and any admission required for this
- Epididymo-orchitis and any admission required for this
- Dysuria
- Debris in urine and any admission required for this
- Haematuria and any admission required for this
- Erectile dysfunction and any other sexual sequelae side-effects such as dry orgasm, lack of orgasm, poor libido
- Urinary incontinence
- Rectal discomfort, bleeding, diarrhoea
- Recto-urethral fistula and any operations required for this
- Lethargy, tiredness, poor appetite
- Urethral stricture and any operations required for this
- Transurethral resection of prostate and any operations required for this
- Operations required for symptoms of bladder outlet obstruction
- Any expected complication related to post-operative course from radical prostatectomy i.e. lymphocoele, bowel injury, haematoma needing percutaneous drainage

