The reasons for ineligibility and withdrawal will be collected and recorded for CHRONOS-A and CHRONOS-B separately. Kaplan-Meier plots will be presented to show time from randomisation to withdrawal for CHRONOS-A and CHRONOS-B separately. Baseline characteristics will be compared between those who completed the Internal Pilot phase of the study, and those who withdrew from the Internal Pilot phase of the study.

Throughout the trial, adverse events will be recorded using the designed eCRFs. Reported adverse events (AEs) and serious adverse events (SAEs) will be listed, and then summarised, by treatment arm, in terms of severity grade (using v4.0 CTCAE grading) and causal relationship to treatment, for CHRONOS-A and B separately. Expected adverse events which are not to be reported as SAEs are listed in Appendix 1.

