15. Appendix 1 – List of Expected Adverse Events that may require hospitalisation and Serious Adverse Events that will not require reporting as SAEs but will be collected

- Urinary retention and any admission required for this
- Urinary tract infection and any admission required for this
- Epididymo-orchitis and any admission required for this
- Dysuria
- Debris in urine and any admission required for this
- Haematuria and any admission required for this
- Erectile dysfunction and any other sexual sequelae side-effects such as dry orgasm, lack of orgasm, poor libido
- Urinary incontinence
- Rectal discomfort, bleeding diarrhoea
- Recto-urethral fistula and any operations required for this
- Lethargy, tiredness, poor appetite
- Urethral stricture and any operations required for this
- Transurethral resection of prostate and any operations required for this
- Operations required for symptoms of bladder outlet obstruction
- Any expected complication related to post-operative course from radical prostatectomy i.e. lympocoele, bowel injury, haematoma needing percutaneous drainage
- Expected toxicity from systemic therapy such as neutropenia, neutropenic sepsis, weight gain, decreased libido, breast tenderness, metabolic syndrome, lethargy, fatigue, osteoporosis, nausea and vomiting, diarrhoea, constipation, muscle/joint pains and hair loss.
- Bowel stricture post radiotherapy, and procedures required for this.

16. Appendix 2 - PROMS

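### SAP 8.3 and footnote 2 of Tables 2.18 and 2.19 turn an exemption from SAE reporting into an exclusion from the by-arm adverse-event summaries

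*SAP*

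**What the plan says.** The restriction appears in three places in the SAP. Section 8.3 lists as a variable "Occurrence of adverse events not listed in Appendix 1". Table 2.18 (adverse events by severity grade and arm) and Table 2.19 (by relationship to treatment and arm) both carry a footnote 2 stating that the expected events in Appendix 1 will not be reported.

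Elsewhere the same list has a narrower purpose. Protocol 7.3 introduces it as "List of expected adverse events that may require hospitalisation and serious adverse events that will not require reporting as SAEs but will be collected". The heading of SAP Appendix 1 keeps that meaning: "Serious Adverse Events that will not require reporting as SAEs but will be collected". SAP 9.3 says "Expected adverse events which are not to be reported as SAEs are listed in Appendix 1". SAP 8.2 also says that the listed events are collected.

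The planned analyses contain no exclusion. For the pilot, Protocol 8.3 plans to analyse how often adverse events occur in each arm. SAP 9.2 plans adverse-event summaries by arm and by site in all randomised patients.

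Appendix 1 is broad. Its entries include "Erectile dysfunction and any other sexual sequelae side-effects such as dry orgasm", "Urinary incontinence", "Recto-urethral fistula and any operations required for this" and "Urethral stricture and any operations required for this". It also covers urinary retention, urinary infection, rectal symptoms, bowel stricture, post-prostatectomy complications and expected toxicity of systemic therapy.

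**The concern.** Under the protocol, the list decides which events skip expedited SAE handling. Under SAP 8.3 and the two footnotes, it decides which events are left out of the adverse-event tables. These are different rules, and only the first is in the protocol.

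The list holds most of the harms that the protocol expects from treatment. Protocol 1.4 expects less incontinence, erectile dysfunction and bowel trouble with focal therapy than with radical therapy. For the CHRONOS-B drug arms it names weight gain, reduced libido, breast tenderness, gynaecomastia and hair loss, and all of these except gynaecomastia are named in Appendix 1. A committee reading Tables 2.18 and 2.19 could take the arms to have similar and low toxicity because the expected toxicity had been filtered out.

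**Working it through.** No sample size, power or error rate is involved, so there is no plan figure to reproduce. The check is of the text, with a small calculation for scale.

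**1. What each place does with an Appendix 1 event**

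| Place | Treatment of Appendix 1 events |
|---|---|
| Protocol 7.3 | Not reported as SAEs; collected |
| Protocol 8.3, pilot analysis | Adverse events by arm; no exclusion |
| SAP 8.2 | Not reported as SAEs; collected |
| SAP 8.3 | Outside the adverse-event variable |
| SAP 9.2 | Adverse events by arm and site; no exclusion |
| SAP 9.3 | Not reported as SAEs; adverse events summarised by arm, grade and causality |
| Table 2.17 | Line listing of all adverse events; no exclusion footnote |
| Tables 2.18 and 2.19 | Not reported (footnote 2) |
| Tables 2.20 to 2.22 (SAEs) | No exclusion footnote, but Protocol 7.3 keeps these events from being reported as SAEs |
| Appendix 1 heading | Not reported as SAEs; collected |

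The exclusion in 8.3 and the two footnotes therefore conflicts with the protocol and with the SAP's own 9.2 and 9.3.

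**2. Following one event through the tables**

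Take a recto-urethral fistula that needs an operation. It is in Appendix 1, so under Protocol 7.3 it is not reported as an SAE and does not reach Tables 2.20 to 2.22. Under SAP 8.3 and footnote 2 it does not reach Tables 2.18 and 2.19. It is left as a line in Table 2.17.

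**3. What the questionnaires recover**

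SAP 9.4 summarises IIEF15, EPIC-26 and EPIC urinary scores by arm at screening and 3 months. The domains cover urinary incontinence, irritative and obstructive symptoms, bowel, sexual function and hormonal symptoms. They give scores, not event counts, CTCAE grades or causality. No scored domain is a measure of fistula, stricture, infection or surgical complications. Retention likewise gets no event count.

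**4. Scale, for illustration only**

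Inputs: 30 men per CHRONOS-A pilot arm (Protocol 3.2, SAP 6.2.3) and the rates that Protocol 1.1 sets side by side for focal and radical treatment. Expected men = 30 × rate.

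- Erectile dysfunction, surgery: 30 × 0.30 to 30 × 0.60 = 9 to 18
- Erectile dysfunction, radiotherapy: 30 × 0.50 to 30 × 0.60 = 15 to 18
- Erectile dysfunction, focal: 30 × 0.05 to 30 × 0.15 = 1.5 to 4.5
- Incontinence, surgery: 30 × 0.05 to 30 × 0.20 = 1.5 to 6
- Urinary dysfunction, radiotherapy: the same rates, 1.5 to 6
- Incontinence, focal: 30 × 0.01 to 30 × 0.02 = 0.3 to 0.6

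The surgery and radiotherapy lines each assume that the whole radical arm has that treatment. The opening paragraph of Protocol 1.1 gives 10–20% incontinence for radical treatment; the 5–20% used here is the figure set directly against focal therapy. The protocol does not link these background rates to the pilot's 3-month minimum follow-up, so actual counts may differ. Whatever the counts, Tables 2.18 and 2.19 as footnoted would show none of these events.

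These two harms are also the ones that the questionnaires cover best. For retention, infection, fistula and stricture, which are lost from every by-arm summary, the documents give no expected rate, so that loss cannot be sized.

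**The case against.** The strongest reply is that this is a drafting slip with limited effect. Most of the SAP, including 8.2, 9.2, 9.3 and the Appendix 1 heading, already states or implies the right rule. The footnote could be shorthand for events not reported as SAEs. Table 2.17 shows treatment group, severity grade, relationship, outcome and a seriousness flag for each event, and with 60 men per trial it can be read through. The questionnaires show urinary, sexual, bowel and hormonal function by arm. The tables are descriptive, and SAP 9.8 describes the safety analysis as a tabulation of SAEs.

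Much of this stands, and it limits the consequence. It does not remove the conflict. SAP 8.3 is explicit, and a programmer working from it would drop these events. A line listing is not an arm summary, and questionnaire scores are not graded events. SAP 9.8 does not displace the by-arm adverse-event summaries that 9.2, 9.3 and Protocol 8.3 plan.

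A reader might also infer three stronger points that the documents do not support:

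- **The main harms vanish from the pilot report.** They do not: the listing and the questionnaire tables remain.
- **The decision to proceed is compromised.** The progression criteria in SAP 9.3 and Section 11 use compliance and recruitment. No adverse-event count enters them.
- **The SAP removed these events from the SAE tables.** That follows from Protocol 7.3; the SAE tables carry no exclusion footnote.

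**Conclusion.** The point holds as a conflict between SAP 8.3 with footnote 2 and the rest of the plan. Followed literally, two by-arm tables, severity and causality, would omit every event on the Appendix 1 list. The unrecovered loss is of event-type harms: retention, infection, recto-urethral fistula, stricture, prostatectomy complications and most drug toxicity would have no event summary by arm. Incontinence, erectile, bowel and hormonal symptoms would lose counts, grades and causality but stay visible as scores.

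The effect is on the safety summaries and not on the go/no-go decision. The conclusion assumes that Table 2.17 is produced as titled, with all adverse events, and that the footnotes are applied as worded. If they were meant only as a reminder about SAE reporting, the harm is confined to ambiguous wording, but 8.3 would still need to change.

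**What to change.** 1. In SAP 8.3, change the line to: *Occurrence of all adverse events, including those listed in Appendix 1.*
2. Delete footnote 2 from Tables 2.18 and 2.19, or reword it to: *not reported as SAEs but included here.*
3. Add by-arm counts of Appendix 1 events, with a separate count of those that met a seriousness criterion, because Protocol 7.3 keeps them out of the SAE tables.

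This brings the SAP into line with Protocol 8.3 and its own 9.2 and 9.3. The protocol already requires the events to be collected, so the cost is SAP wording and slightly longer tables. The change should be made before the tables are programmed.
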